2. STATISTICAL HYPOTHESES

The primary objective of this study is to assess the safety and tolerability of single IV and SC doses of GSK3888130B in healthy participants.

No formal hypotheses are being tested in this study.

2.1. Multiplicity Adjustment

There will be no adjustments for multiplicity in this study.

3. ANALYSIS SETS

Analysis Set	Definition / Criteria	Analyses Evaluated
Screened	
 • All participants who signed the ICF and are screened for eligibility. 	Study Population
Enrolled	
 • All participants in the Screened analysis set who are entered into the study. • Note screening failures (who never passed screening even if rescreened) and ‘reserved’ or ‘not used’ participants are excluded from the Enrolled analysis set as they did not enter the study. 	Study Population
Randomised	
 • All participants who are randomly assigned to study intervention in the study. 	Study Population
Safety	
 • All participants who received study intervention. • Participants will be analysed according to the study intervention administered. 	
 • Study Population • Safety
Pharmacokinetic (PK)	
 • All participants in the Safety analysis set who had received an active study intervention and had at least 1 non-missing post dose PK assessment (Non-quantifiable [NQ] values will be considered as non-missing values). • Data will be reported according to the actual study intervention. 	PK
Pharmacodynamic (PD)	
 • All participants in the Safety analysis set who had at least one post baseline PD result. • Data will be reported according to the actual study intervention. 	
 • PD/Biomarker

4. STATISTICAL ANALYSES

4.1. General Considerations

4.1.1. General Methodology

Participants who prematurely withdraw from study may be replaced.

Unless otherwise specified, the Screened, Enrolled, Randomised or Safety Analysis Sets will be used for all Study Population analyses, the Safety Analysis Set will be used for all Safety analyses, the PK Analysis Set will be used for all Pharmacokinetic analyses and the PD Analysis Set will be used for all Pharmacodynamic/ Biomarker analyses.

For all summaries, statistical analyses and plots, Placebo participants will be pooled across all cohorts in which the endpoint was collected, except for the following endpoints:

- Cellular Biomarkers, CCI [REDACTED] and CCI [REDACTED] (Section 4.4.3): Placebo data will be pooled across Cohorts 1,2,3,4 and 7 CCI [REDACTED]
[REDACTED]
[REDACTED].
- CCI [REDACTED] Placebo data will be summarised by cohort since there are limited timepoints relative to the CCI [REDACTED] which are common to these cohorts.

CCI [REDACTED]
[REDACTED]
[REDACTED]

CCI [REDACTED]
[REDACTED]

Absolute baseline values will be included in all change from baseline or ratio to baseline summaries. Line plots will be produced on absolute values unless otherwise specified.

95% equal tailed Credible Intervals (CrI) will be used for statistical analyses unless otherwise specified.

Summary tables will provide the following descriptive statistics as a minimum, unless otherwise specified:

- For continuous untransformed data (or where many zeros exist in the data): n, mean, 95% Confidence Intervals (CI), standard deviation (SD), median, minimum and maximum. Number of Zeros may also be added as an additional statistic, if deemed appropriate.
- For continuous log-normally distributed data: n, geometric mean, 95% CI of the geometric mean, standard deviation on the log scale (SD (log)), %CVb (only for PK Parameters), median, minimum and maximum.
- For categorical data: number and percentage of participants in each category.

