6. STUDY INTERVENTION(S) AND CONCOMITANT THERAPY

Study intervention is defined as any investigational intervention(s), marketed product(s), placebo, or medical device(s) intended to be administered to a study participant according to the study protocol.

6.1. Study Intervention(s) Administered.

	Study Intervention		CCI [REDACTED]	
ARM Name	GSK3888130B	Placebo	CCI [REDACTED]	CCI [REDACTED]
Intervention Name	GSK3888130B Injection	Placebo	CCI [REDACTED] [REDACTED]	CCI [REDACTED]
Type	Drug	Drug	CCI [REDACTED] [REDACTED]	CCI [REDACTED]
CCI [REDACTED]		CCI [REDACTED] [REDACTED] [REDACTED] [REDACTED] [REDACTED] [REDACTED] [REDACTED]		CCI [REDACTED] [REDACTED] [REDACTED] [REDACTED] [REDACTED] [REDACTED]
Unit Dose Strength(s)	CCI [REDACTED] mg/mL	0.9%	CCI [REDACTED] [REDACTED] [REDACTED]	CCI [REDACTED] [REDACTED]
Dosage Level(s)	IV: CCI [REDACTED] mg SC: CCI [REDACTED] mg	Volume to match volume of	CCI [REDACTED] [REDACTED] [REDACTED]	CCI [REDACTED] [REDACTED] [REDACTED]

For the IV cohorts GSK3888130B is planned to be infused over an approximate duration of **CCI**. GSK3888130B can be diluted in saline (0.9% sodium chloride) prior to administration.

For the SC cohorts: the appropriate volume of GSK3888130B will be injected using a syringe at no more than **cc1** per injection. Up to **cc1** injections per dose may be needed.

The same volume of saline (used as placebo) will be infused (IV) or injected (SC) in the same manner as the corresponding GSK3888130B administrations in that cohort.

Infusion durations may vary by cohort due to the wide range of dose concentrations planned to be administered. Where possible volumes and infusion rates will be kept constant. Infusion durations maybe modified based on emerging safety and PK data.

Full instructions for dilution of study intervention to dose concentrations to be administered will be provided in the Pharmacy Manual.

CCI

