9.2. Sample Size Determination

Approximately 54 participants will be recruited to seven single ascending dose cohorts. Five participants will be randomized to either GSK3888130B or placebo in 3:2 ratio in cohorts 1 and 2. Eight participants will be randomized to either GSK3888130B or placebo in 3:1 ratio in all other cohorts, CCI

No formal statistical techniques were used to calculate the sample size for this study; it has been determined to allow preliminary assessment of safety, tolerability, PK and PD. However, as a key secondary endpoint, considerations has been given to the ratio to baseline of the PD biomarker Bcl-2. It is assumed that this endpoint is \log_e normally distributed. Based on 6 participants from the highest GSK3888130B dosed cohort and 14 placebo participants pooled across all cohorts, the probability of different true inhibition (GSK3888130B vs. placebo) thresholds of interest is given in the Table below. A non-informative prior distribution and a maximum between participant SD (\log_e scale) of 0.3 is assumed for both GSK3888130B and placebo arms.

True Inhibition thresholds	Probability of Meeting Thresholds Given the Following True Inhibition
CCI	CCI

CCI

CCI

CCI

CCI

Note: "Enrolled" means a participant's, or their legally acceptable representative's, agreement to participate in a clinical study following completion of the informed consent process and screening. Potential participants who are screened for the purpose of determining eligibility for the study, but do not participate in the study, are not considered enrolled, unless otherwise specified by the protocol.

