1.2. Study Design

Overview of Study Design and Key Features					

Single Ascending Dose (SAD) design in healthy volunteers: planned IV and SC dosing in an interlocking design.
 					
Design Features	
 Phase 1, single centre, randomised, double-blind, placebo controlled, dose escalation study comprising of seven planned SAD cohorts of GSK3888130B over a range of dose levels (from ccI mg to ccI mg) in healthy participants. ccI mg IV ccI mg SC ccI mg IV. 
Participants will attend a screening visit within 28 days of study intervention. In participants who require an influenza vaccination and/or SARS-CoV-2 vaccination or booster, the screening window may be increased to 60 days.
 
Participants will receive study intervention on Day 1. For the IV cohorts, participants will remain in the unit for cc days and for the SC cohorts for cc days.
 
All participants will then attend the clinic for up to cc outpatient visits after dosing, over the course of ccI days, for safety assessments and sample collection and will receive two follow-up telephone calls; the first will be ccI days post last study visit and the second will be ccI days post last study visit. If required, additional follow-up visits may be scheduled.
				
Study intervention	
  
 Cohorts	Study Intervention	
   
 Cohort 1 – IV Dose	GSK3888130B cc mg vs Placebo	
  
	Cohorts	Study Intervention	Cohort 1 – IV Dose	GSK3888130B cc mg vs Placebo
Cohorts	Study Intervention				
Cohort 1 – IV Dose	GSK3888130B cc mg vs Placebo				

Overview of Study Design and Key Features		
	Cohort 2 – IV Dose	GSK3888130B [REDACTED] mg vs Placebo
	Cohort 3 – SC Dose	GSK3888130B [REDACTED] mg vs Placebo
	Cohort 4 – IV Dose	GSK3888130B [REDACTED] mg vs Placebo
	Cohort 5 – SC Dose	GSK3888130B [REDACTED] mg vs Placebo
	Cohort 6 – IV Dose	GSK3888130B [REDACTED] mg vs Placebo
	Cohort 7 – IV Dose	GSK3888130B [REDACTED] mg vs Placebo
Study intervention Assignment	
 The study will aim to recruit 54 participants into seven SAD cohorts. Cohort 1 and 2: Eligible participants will be randomised to receive either GSK3888130B or placebo in a 3:2 ratio comprising of five participants. Cohort 3 to 7: Eligible participants will be randomised in a 3:1 ratio comprising of eight participants, except for cohort 6 which [REDACTED] 	

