4.2.1. Adverse Events

An adverse event (AE) is considered study intervention emergent if the AE onset date is on or after study intervention start date. All AE summaries will be based on study intervention emergent events unless otherwise specified. SAE summaries will be based on all SAEs reported regardless of whether they meet the definition of study intervention emergent or not. All AE and SAE summaries will be by System Organ Class (SOC) and Preferred Terms (PT) or only by PT, unless otherwise specified.

Adverse events will be coded using the standard Medical Dictionary for Regulatory Affairs (MedDRA dictionary) and graded by the investigator according to the National Cancer Institute - Common Terminology Criteria for Adverse Events (NCI-CTCAE, version 5).

An overview summary of AEs, including counts and percentages of participants, will be summarized for the following categories and subcategories.

- AE
 - Any AEs
 - AEs related to study intervention
 - AEs leading to study withdrawal
- SAE
 - Any SAEs
 - SAEs related to study intervention

A study intervention-related AE/SAE is defined as an AE for which the investigator classifies the possible relationship to study intervention as “Yes”. If relationship to study intervention is missing then worst-case approach will be applied (i.e. missing will be handled in the same way as ‘Yes’).

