4.2.1.1. Adverse Events of Special Interest

There are no adverse events of special interest identified for this study.

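### On the legible SAP, IV and SC placebo are pooled for adverse events, so only 4 of 14 or 15 placebo participants match the SC cohorts by route for injection-site reactions

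*SAP*

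**What the plan says.** SAP 4.1.1 covers all summaries, analyses and plots: "Placebo participants will be pooled across all cohorts in which the endpoint was collected, except for the following endpoints". Two exceptions can be read. One pools cellular biomarkers and some redacted endpoints over cohorts 1, 2, 3, 4 and 7, which still mixes routes. The other concerns an endpoint whose name is redacted: "Placebo data will be summarised by cohort since there are limited timepoints relative to the" (the sentence continues). Its reason is timing, not route. Adverse events are collected in every cohort (Protocol 8.3.1), so the default applies to them.

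SAP 4.2.1 sets the layout: "All AE and SAE summaries will be by System Organ Class (SOC) and Preferred Terms (PT) or only by PT, unless otherwise specified". SAP 4.2.1.1 adds: "There are no adverse events of special interest identified for this study". SAP 4.5.1 plans no formal subgroup analysis.

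On the placebo itself, Protocol 6.1 states: "The same volume of saline (used as placebo) will be infused (IV) or injected (SC) in the same manner" as the active dose of that cohort. For SC dosing, several "injections per dose may be needed"; the number is redacted. SAP 1.2 lists cohorts 3 and 5 as SC and the other five as IV. Protocol 2.3.1 names injection-site reactions as a risk to be closely monitored, and the primary objective covers both IV and SC doses.

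**The concern.** Protocol 4.2 includes a placebo arm so that effects of treatment can be told apart from effects that would occur anyway. For local reactions, the needle, the volume and the route are part of what would occur anyway. Most people in the pooled placebo column had an IV infusion and no SC injection. If saline provokes local signs more often under the skin than through a vein, the pooled percentage is too low a reference for the SC cohorts, and a reaction to the procedure can read as a reaction to the drug. At stake is how one part of a primary-endpoint display is read.

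**Working it through.** **Inputs**

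- Cohorts 1 and 2: 5 participants each at 3:2, so 2 placebo each, IV (Protocol 9.2, SAP 1.2).
- Cohorts 3 to 7: "Eligible participants will be randomised in a 3:1 ratio comprising of eight participants, except for cohort 6 which" differs (detail redacted). Eight at 3:1 gives 2 placebo and 6 active. Cohorts 3 and 5 are SC; 4, 6 and 7 are IV.
- Stated total: 54. Stated pool: "14 placebo participants pooled across all cohorts" (Protocol 9.2, repeated in SAP 5).
- Rates of site reaction to saline, by either route: not given. They are assumed below.

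**Step 1. Reproduce the stated placebo count.** With 8 in cohort 6, placebo = 7 × 2 = 14, which matches, but the total is 2 × 5 + 5 × 8 = 50. To reach 54, cohort 6 needs 54 − 10 − 4 × 8 = 12. At 3:1 (assumed) that is 3 placebo, so the pool is 6 × 2 + 3 = 15. Both sizes are carried forward.

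**Step 2. Route-matched share.** SC placebo = 2 + 2 = 4. Cohort 6 is IV, so this does not depend on it. IV placebo = 10 or 11. The SC share is 4/14 = 28.6% or 4/15 = 26.7%.

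**Step 3. Understatement of the SC placebo rate.** Let p be the SC saline rate, r the IV rate divided by the SC rate, and N the pool. The expected pooled rate is [4p + (N − 4)rp]/N, so the SC rate exceeds it by the factor N / [4 + (N − 4)r].

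| r (assumed) | N = 14 | N = 15 |
|---|---|---|
| 0 | 14/4 = 3.50 | 15/4 = 3.75 |
| 0.2 | 14/6 = 2.33 | 15/6.2 = 2.42 |
| 0.5 | 14/9 = 1.56 | 15/9.5 = 1.58 |
| 1 | 1.00 | 1.00 |

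**Step 4. The same in percentage points.** With no drug effect, the apparent excess in an SC active column is p(N − 4)(1 − r)/N. That is 0.71p to 0.73p at r = 0, 0.36p to 0.37p at r = 0.5, and 0 at r = 1. The only incidence in the documents is the 1–5% in Protocol 2.3.1, which is for other monoclonal antibodies. If it is assumed for SC saline, the excess is 0.7 to 3.7 points at r = 0 and 0.4 to 1.8 points at r = 0.5. For scale, one participant is 1/14 = 7.1 or 1/15 = 6.7 points of the pooled column, and 1/6 = 16.7 points of one SC active cohort.

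**Step 5. How one event would appear.** One reaction among the 4 SC placebo participants and none among IV placebo reads 25% by route, but 7.1% or 6.7% pooled.

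**The case against.** The case against acting is strong, and most of it stands.

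- **No decision depends on it.** No hypothesis is tested. Protocol 9.4.3 rests interpretation mainly on the relationship reported by investigators, who are blind to allocation. SAP 4.6 has the site supply safety reports for escalation, and the legible halt rules in Protocol 7.2.5 count participants.
- **Four people cannot estimate a rate.** On the assumed 1–5%, the chance of no reaction among them is 0.99^4 = 96% to 0.95^4 = 81%. The SC placebo count is then zero with or without a split. A reader might infer that replacing a zero out of 14 or 15 with a zero out of 4 is itself evidence of benefit. It is not: only the denominator changes, and the minimum output in SAP 4.1.1 for categorical data is a number and a percentage, with no interval.
- **A single SC placebo group is not fully matched either.** Saline volume follows the active dose of each cohort, and the number of injections may differ between cohorts 3 and 5. A full match leaves 2 people per cohort. Nor is there a readable plan to combine the SC active participants: they are two columns of 6.
- **The split may already exist.** Redacted blocks follow the exceptions in SAP 4.1.1, and SAP 4.2.4 places full details of the safety displays in the Output and Programming Specification, which is not available here.

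These points limit the size and make the change optional. They do not alter the legible rule, which gives an SC reaction a reference group that is mostly IV.

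**Conclusion.** The point holds as a cheap improvement to a display. On the legible text, each SC cohort's site reactions are set beside a placebo column in which 4 of 14 or 15 people had SC saline. The understatement is about 1.6-fold at an assumed IV:SC ratio of 0.5 and nil at equal rates. The count of 4 is firm for the planned cohorts; the 15 assumes 12 people at 3:1 in cohort 6, and every percentage-point figure assumes a saline rate.

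Three stronger readings are not supported.

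- **That a 3.5- to 3.75-fold understatement is to be expected.** It needs no IV reactions at all, whereas Protocol 8.2.6 describes local signs along the vein.
- **That pooling could conceal harm from SC dosing.** Where SC is the more reactive route, the error runs the other way and makes SC active look worse against placebo.
- **That safety decisions are unsound.** No legible halt or escalation rule uses a placebo percentage.

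**What to change.** In SAP 4.1.1 and 4.2.1, keep the pooled placebo column. For a short list of injection-site and infusion-site preferred terms, add n/N for Placebo IV and Placebo SC to the adverse event summary, as two columns or a footnote. Label these counts supportive, because SC placebo is about 4 people and may mix injection volumes or numbers across cohorts 3 and 5. Blinded staff should fix the list before unblinding, since Protocol 6.3 unblinds the Statistics and Programming team for dose-escalation outputs. If the output specification or the redacted text already provides this, a cross-reference in SAP 4.2.1 is enough.

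The cost is agreeing the list, two columns or a footnote in one table, and two or three sentences in the SAP. No new data are needed. The downside is a small column that shows route but could be over-read as a rate, hence the label.

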4.1.2. Model Checking and Diagnostics

The analyses will be conducted in the Bayesian framework. Models will be fitted by MCMC simulations using non-informative priors.

A thinning sample may be used to aid convergence; where k is the thinning ratio and the number of samples are a minimum of $10,000 * k$. For example, 100,000 MCMC samples may be generated with a thin of 10, providing 10,000 samples to be used for the estimate of the posterior distribution. A burn-in of 5,000 samples will be used by first intent.

The following list of convergence diagnostics will be applied for each parameter (diagnostic checking outputs will be stored in the refdata folder in HARP in the relevant reporting effort):

- The Monte Carlo Standard Errors (MCSE) should be compared with the standard deviation of the posterior distribution (SD) to ensure that only a fraction of the posterior variability is due to the simulation. The number of samples generated, and/or the thinning may be increased to reduce the ratio of the MCSE/SD as deemed necessary.
- Trace plots of samples versus the simulation index will be visually inspected to assess some aspects of convergence. The centre of the chain should appear stable with very small fluctuations, i.e., the distribution of points should not change as the chain progresses and the posterior mean and variance are relatively constant.
- Autocorrelation plots will be visually inspected to assess degree of autocorrelation (should decline rapidly and show no oscillation patterns).
- Density plots of the posterior for the model parameters will be plotted (should be smooth and with a single hump).

If the model is not deemed to have converged then increasing the number of MCMC samples and/or the thinning will be explored. The blocking of the parameters will also be considered.

4.1.3. Baseline Definition

For all endpoints the baseline value will be the latest pre-dose assessment (unless otherwise specified) with a non-missing value, including those from unscheduled visits. If time is not collected at Day 1:

- If a pre-dose sample collection is the only scheduled visit (as per the schedule of activities table in the protocol), then Day 1 will be used as baseline.
- Otherwise, if an assessment prior to Day 1 is available, this will be used as baseline.
- Otherwise, baseline will be set to missing.

4.1.3.1. Derivations and Handling of Missing Baseline Data

For untransformed data, change from baseline at each time point is expressed as a difference. For \log_e transformed data, change from baseline will be expressed as a ratio. For individual gene data, change from baseline will be expressed as a fold change.

Definition	Reporting Details
Change from Baseline	= Post-Baseline Visit Value – Baseline Value
Ratio to Baseline	= Post-Baseline Visit Value / Baseline Value OR = Exponential of (Log (Post-Baseline Visit Value) – Log (Baseline Value))
Fold Change Relative to Baseline	= 2 to the power of (Post-Baseline Visit Value* – Baseline Value*) [*note that individual gene data is received on the log ₂ scale]

Unless otherwise specified, if baseline data is missing, no derivation will be performed and baseline will be set to missing.

4.2. Safety Analyses

The primary objective of this study is to assess the safety and tolerability of single IV and SC doses of GSK3888130B.

4.2.1. Adverse Events

An adverse event (AE) is considered study intervention emergent if the AE onset date is on or after study intervention start date. All AE summaries will be based on study intervention emergent events unless otherwise specified. SAE summaries will be based on all SAEs reported regardless of whether they meet the definition of study intervention emergent or not. All AE and SAE summaries will be by System Organ Class (SOC) and Preferred Terms (PT) or only by PT, unless otherwise specified.

Adverse events will be coded using the standard Medical Dictionary for Regulatory Affairs (MedDRA dictionary) and graded by the investigator according to the National Cancer Institute - Common Terminology Criteria for Adverse Events (NCI-CTCAE, version 5).

An overview summary of AEs, including counts and percentages of participants, will be summarized for the following categories and subcategories.

- AE
 - Any AEs
 - AEs related to study intervention
 - AEs leading to study withdrawal
- SAE
 - Any SAEs
 - SAEs related to study intervention

A study intervention-related AE/SAE is defined as an AE for which the investigator classifies the possible relationship to study intervention as “Yes”. If relationship to study intervention is missing then worst-case approach will be applied (i.e. missing will be handled in the same way as ‘Yes’).

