Procedure	Screening (up to 28 days before Day 1) ¹	Day -1	E.D	Follow-up (CCI [REDACTED] days post last study visit)	Follow-up (CCI [REDACTED] days post last study visit)	Notes E.D = early discontinuation/withdrawal 1. In participants who require an influenza vaccination and/or SARS-CoV-2 booster, the screening window may be increased to 60 days. This extended screening window applies only to those participants, and if their initial screening assessments are conducted more than 28 days prior to Day 1, screening assessments will be repeated within 28 days of Day 1.
Breath alcohol test, smoking breath test and urine drug screen	X	X				
SARS-CoV-2 Test	<=====>					As per local guidelines.
Confirmation of postmenopausal status in females if required.	X					FSH and oestradiol test.
AE Review			X	X	X	
Blood collection for Immunogenicity testing			X			
SAE Review	X	X	X	X	X	Collected from signing the informed consent form.

Procedure	Screening (up to 28 days before Day 1) ¹	Day -1		Follow-up (CCI days post last study visit)	Follow-up (CCI days post last study visit)	Notes E.D = early discontinuation/withdrawal 1. In participants who require an influenza vaccination and/or SARS-CoV-2 booster, the screening window may be increased to 60 days. This extended screening window applies only to those participants, and if their initial screening assessments are conducted more than 28 days prior to Day 1, screening assessments will be repeated within 28 days of Day 1.
CCI		CCI				

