8.3.1. Time Period and Frequency for Collecting AE and SAE Information

- All SAEs will be collected from the signing the informed consent form until the final follow-up visit at the time points specified in the SoA (Section 1.3).
- All SARs to study procedure/GSK products will be reported from the signing of the informed consent form (ICF) until the final follow-up visit at time points specified in the SoA (Section 1.3).
- All AEs will be collected from the start of intervention until the final follow-up visit at the time points specified in the SoA (Section 1.3).
- Medical occurrences that begin before the start of study intervention but after obtaining informed consent will be recorded as Medical History/Current Medical Conditions not as AEs.
- All SAEs will be recorded and reported to the Sponsor or designee immediately and under no circumstance should this exceed 24 hours, as indicated in [Appendix 3](#). The Investigator will submit any updated SAE data to the Sponsor within 24 hours of it being available.
- Investigators are not obligated to actively seek information on AEs or SAEs after the conclusion of the study participation. However, if the Investigator learns of any SAE, including a death, at any time after a participant has been discharged from the study, and he/she considers the event to be reasonably related to the study intervention or study participation, the Investigator must promptly notify the Sponsor.

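### SAP 4.2.1 counts AEs from dosing but SAEs from consent, so a pre-dose SAE in a participant who is later dosed appears in a treatment column

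*SAP*

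**What the plan says.** SAP 4.2.1 sets three rules:

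- Emergence: "An adverse event (AE) is considered study intervention emergent if the AE onset date is on or after study intervention start date".
- AEs: "All AE summaries will be based on study intervention emergent events unless otherwise specified".
- SAEs: "SAE summaries will be based on all SAEs reported regardless of whether they meet the definition of study intervention emergent or not".

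The overview table in the same section then places participants with any AE and participants with any SAE in one display. Each has a sub-row for events related to study intervention. A missing relationship is handled as related.

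Protocol 8.3.1 uses two collection periods. For SAEs, "All SAEs will be collected from the signing the informed consent form until the final follow-up visit". For AEs, "All AEs will be collected from the start of intervention until the final follow-up visit". The schedule of activities (protocol 1.3.1) marks SAE review at Screening and Day -1, with the note "Collected from signing the informed consent form". Protocol 8.3.1 also says that "Medical occurrences that begin before the start of study intervention but after obtaining informed consent will be recorded as Medical History/Current Medical Conditions", and adds that these are not AEs.

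SAP section 3 defines the Safety set as "All participants who received study intervention" and analyses those participants by the intervention administered. SAP 4.1.1 pools placebo across cohorts.

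**The concern.** Occurrence of AEs and SAEs is the first primary endpoint, and its two halves are counted over different periods in the same table. An SAE between consent and dosing says nothing about GSK3888130B or placebo, yet it would sit in the column for whichever the participant later received. The pre-dose period is not always empty: participants who need it receive an influenza vaccine during an extended screening window, at least 30 days before dosing.

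The groups are very small, so a single such event would be conspicuous. A participant whose only event was a pre-dose SAE would appear in the any-SAE row but not in the any-AE row. The visible SAP text plans no split, flag or footnote that would explain this.

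**Working it through.** The plan gives no figure of its own on this point, so there is nothing to reproduce. The check sets the rules side by side and then gives the scale.

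**1. Counting periods**

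| | AEs | SAEs |
|---|---|---|
| Collected from (protocol 8.3.1) | start of intervention | consent |
| Counted in summaries from (SAP 4.2.1) | start of intervention | consent |
| Pre-dose period counted | none | up to 28 days; up to 60 if vaccination is needed |

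**2. Who is affected.** The Safety set holds dosed participants only. An SAE in a screen failure or an unused reserve does not enter. An SAE after consent in someone who is still dosed does enter, under the intervention given.

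**3. Subset check.** Take a participant with one SAE at Day -10 and no event after dosing. The SAE is not emergent, so the any-AE count is 0, but the any-SAE count is 1. The subset relation fails for that participant. For the SAE count of a whole column to exceed its AE count, participants with any SAE must outnumber those with any emergent AE in that group.

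**4. Size of one event.** The share is 1/n for the column.

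- Cohort 1 or 2, five participants at 3:2, so n = 3 active: 1/3 = 33.3%.
- A cohort of eight at 3:1, so n = 6 active: 1/6 = 16.7%.
- Pooled placebo, n = 14 (SAP section 5): 1/14 = 7.1%.

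The size of cohort 6 is redacted. From the total it is inferred as 54 - 2 x 5 - 4 x 8 = 12. At 3:1 that is 9 active and 3 placebo, which gives 3 + 3 + 4 x 6 + 9 = 39 active of 54 and 15 placebo, against the stated 14. Keeping 14 placebo gives 40 active. This split is an inference and changes little: 1/15 = 6.7%, still about 7%.

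**5. How likely.** The documents give no rate of pre-dose SAEs. Let p be an assumed chance per dosed participant. The chance of at least one among 54 is 1 - (1 - p)^54.

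| Assumed p | Chance of at least one |
|---|---|
| 0.05% | 2.7% |
| 0.1% | 5.3% |
| 0.5% | 23.7% |
| 1% | 41.9% |

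Eligibility is checked again on Day -1, which favours the lower rows.

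**6. Route to the related row.** An SAE with missing relationship is counted as related (SAP 4.2.1). Because the SAE rule has no onset restriction, this would apply to a pre-dose SAE as well.

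**7. Protocol 8.3.1 against itself.** The medical-history line is not limited to non-serious events. Read literally, it takes pre-dose SAEs out of the AE record. The SAE line in the same section and the schedule of activities put them in. The SAP rule has content only under the second reading.

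**The case against.** The rule is explicit and prespecified, and it agrees with an SAE collection period that begins at consent. Counting every collected SAE is the inclusive choice and keeps events linked to study procedures in view. Nothing is tested formally. Detailed displays are left to the Output and Programming Specification, which is not among the documents and may separate pre-dose events.

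Most of that stands. A reader might infer that the SAP contradicts the protocol on SAE collection. It does not: this is an analysis choice.

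A reader might also infer that pre-dose SAEs would be attributed to the drug. The documents do not support that either. The overview has a separate row for related SAEs. Protocol 9.4.3 makes investigator-reported relationship the principal consideration in interpreting safety. Protocol 10.3.3 requires a causality assessment before an SAE is first transmitted, so a missing relationship should be uncommon. An effect on dose escalation does not follow, because the SAE halting rule in protocol 7.2.5 depends on a reasonable possibility of relation to GSK3888130B.

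What does not stand is that prespecification settles the matter. Stating the rule in advance does not make an event before dosing informative about what was given afterwards. The unseen specification might reduce the problem, but the SAP is the governing text and as written it combines the two periods.

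**Conclusion.** The point holds as a weakness in how a primary safety endpoint is tabulated. The AE rows start at dosing and the SAE rows start at consent, so a pre-dose SAE in a dosed participant enters a dose or placebo column and the SAE rows need not nest within the AE rows. It means being counted in a column, not being judged caused by the drug.

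The expected number of such events is small. If one occurs, it reads as 33% in the active group of cohort 1 or 2, 17% in an active group of six, and about 7% in pooled placebo. The probabilities in the working rest on an assumed rate, and the 39 of 54 split is inferred around a redaction. The conclusion depends on neither. It does assume that SAEs before dosing are recorded as SAEs, which one line of protocol 8.3.1 leaves unclear.

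**What to change.** In SAP 4.2.1, base the by-intervention SAE summaries and the SAE rows of the overview on SAEs with onset on or after the start of study intervention. Report all pre-dose SAEs in a separate listing with study day, not by intervention. This also removes pre-dose SAEs from the reach of the missing-relationship rule.

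In protocol 8.3.1, reconcile the medical-history line with SAE collection from consent, so that it is clear how a serious event before dosing is recorded.

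The cost is one SAP sentence and one listing, with a clarification to the protocol text. Collection and expedited reporting are unchanged, and no data are lost.
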